
4.2.2.3 Imipenem/Cilastatin

IMI will be provided as combination therapy with CMS, as a separate infusion. For treatment in severe, life-threatening infections caused by moderately susceptible organisms, a 3- to 4-gram daily dose is recommended for IMI monotherapy. While the infections in this study are anticipated to be serious, imipenem-resistant organisms are the target pathogens for this study and there is no recommended dosing regimen for resistant organisms, since IMI would not be used as monotherapy for imipenem-resistant organisms. IMI is not being used as the primary treatment modality in this study and has been added as part of a combination regimen with CMS (*Note:* additional discussion regarding rationale for combination therapy

of CMS + IMI is included in Section 4.2.2.6). Furthermore, prior to study entry, *in vitro* susceptibility results must show confirmed susceptibility of the pathogens to colistin. For these reasons, as well as in an effort to support blinding feasibility as well as a straightforward safety and efficacy evaluations, the chosen dose for IMI in this study is 500 mg, administered IV once every 6 hours (i.e., 2 gram total daily dose).

The dosage of IMI will be adjusted in patients with renal impairment. Depending on the individual subject's renal function (as determined by actual or estimated creatinine clearance), the total daily dose of IMI may be adjusted. As previously discussed (See Section 4.2.2.1), adjustments for body weight will not be made. Specific dosing guidelines for IMI are included in Section 5.2.1.1, [Table 11](#).

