Twelve (12) hours after the initial loading dose, maintenance dosing will begin and then continue every 12 hours (q12h) thereafter. The maintenance dose of CMS will be based on creatinine clearance according to [Table 12](#). Creatinine clearance may be calculated from serum creatinine concentration by the equation previously provided. It is important to note that a change in the subject's creatinine clearance during IV study therapy could result in dosage adjustments at any time during IV therapy.

Subjects assigned to Treatment Group 1 will receive a matching placebo for CMS on the same schedule as subjects in Treatment Group 2 (first dose upon initiation of therapy followed by q12h maintenance doses beginning 12 hours later). Since Treatment Group 3 is open-label, no placebo will be administered to subjects enrolled into this Treatment Group.

Table 11 Administration Dosage of IMI/REL and IMI According to Renal Function

Creatinine Clearance (mL/min)	IMI/REL^a	IMI
≥ 90	500/250 mg q6h	500 mg q6h
< 90 to ≥ 60	400/200 mg q6h	400 mg q6h
< 60 to ≥ 30	300/150 mg q6h	300 mg q6h
< 30 to ≥ 15	200/100 mg q6h	200 mg q6h
^a IMI/REL is provided as a single vial in a fixed-dose combination; therefore, the dose for each component will be adjusted equally during preparation. For example, a Treatment Group 1 subject who has a creatinine clearance of 50 mL/min should receive a 150 mg q6h dose of REL according to the table. Since the dose is reduced by 50% during preparation, the total mg of IMI would also be reduced by 50%, thus resulting in a 300 mg q6h dose of IMI.		

Table 12 Administration Dosage of Loading and Daily Maintenance Doses of CMS According to Renal Function

Creatinine Clearance (mL/min)	Loading Dose^a	Maintenance Dose^b
≥ 90	300 mg CBA (~720 mg CMS or ~9 million IU)	150 mg CBA (~360 mg CMS or ~4.5 million IU)
< 90 to ≥ 60		150 mg CBA (~360 mg CMS or ~4.5 million IU)
< 60 to ≥ 30		115 mg CBA (~270 mg CMS or ~3.4 million IU)
< 30 to ≥ 15		75 mg CBA (~180 mg CMS or ~2.3 million IU)
CMS = colistimethate sodium; CBA = colistin base activity.		
^a If a loading dose ≥ 200 mg CBA (~470 mg CMS or ~5.9 million IU) was administered prior to study entry, the subject should begin maintenance doses upon initiation of IV study therapy. If the subject has not previously received a loading dose, a loading dose should be provided as described, regardless of the dosage previously administered.		

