^b With the exceptions noted in footnote a, the maintenance dose will be administered 12 hours following administration of the loading dose and will be administered every 12 hours thereafter.		

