Electronic reporting procedures can be found in the EDC data entry guidelines. Paper reporting procedures can be found in the Investigator Trial File Binder (or equivalent).

7.2.1 Definition of an Overdose for This Protocol and Reporting of Overdose to the Sponsor

In this trial, an overdose in study therapy is defined as administration of a total daily dose of IMI/REL in excess of 4 g (IMI) + 2 g (REL) OR a total daily dose of IMI in excess of 4 g per day OR a total daily dose of CMS in excess of the protocol-specified doses in Section 5.2.1.1, [Table 12](#).

If an adverse event(s) is associated with ("results from") the overdose of Sponsor's product or vaccine, the adverse event(s) is reported as a serious adverse event, even if no other seriousness criteria are met.

If a dose of Sponsor's product or vaccine meeting the protocol definition of overdose is taken without any associated clinical symptoms or abnormal laboratory results, the overdose is reported as a non-serious Event of Clinical Interest (ECI), using the terminology "accidental or intentional overdose without adverse effect."

All reports of overdose with and without an adverse event must be reported by the investigator within 24 hours to the Sponsor either by electronic media or paper. Electronic reporting procedures can be found in the EDC data entry guidelines. Paper reporting procedures can be found in the Investigator Trial File Binder (or equivalent).

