7.2.4 Evaluating Adverse Events

An investigator who is a qualified physician will evaluate all adverse events with respect to the elements outlined in [Table 15](#). The investigator's assessment of causality is required for each adverse event. Refer to [Table 15](#) for instructions in evaluating adverse events.

Table 15 Evaluating Adverse Events

Maximum Intensity	Mild	awareness of sign or symptom, but easily tolerated (for pediatric trials, awareness of symptom, but easily tolerated)
	Moderate	discomfort enough to cause interference with usual activity (for pediatric trials, definitely acting like something is wrong)
	Severe	incapacitating with inability to work or do usual activity (for pediatric trials, extremely distressed or unable to do usual activities)
Seriousness	A serious adverse event (AE) is any adverse event occurring at any dose or during any use of Sponsor's product that:	
	†Results in death; or	
	†Is life threatening; or places the subject, in the view of the investigator, at immediate risk of death from the event as it occurred [Note: This does not include an adverse event that, had it occurred in a more severe form, might have caused death.]; or	
	†Results in a persistent or significant disability/incapacity (substantial disruption of one's ability to conduct normal life functions); or	
	†Results in or prolongs an existing inpatient hospitalization (hospitalization is defined as an inpatient admission, regardless of length of stay, even if the hospitalization is a precautionary measure for continued observation. (Note: Hospitalization [including hospitalization for an elective procedure] for a preexisting condition which has not worsened does not constitute a serious adverse event.); or	
	†Is a congenital anomaly/birth defect (in offspring of subject taking the product regardless of time to diagnosis); or	
	Is a cancer (although not serious per ICH definition, is reportable to the Sponsor within 24 hours to meet certain local requirements); or	
	Is associated with an overdose (whether accidental or intentional). Any adverse event associated with an overdose is considered a serious adverse event for collection purposes. An overdose that is not associated with an adverse event is considered a non-serious event of clinical interest and must be reported within 24 hours.	

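### Section 7.2.1 defines overdose by a fixed daily limit for IMI/REL and IMI but by any excess over the renal-tier dose for CMS, and Table 12 gives the CMS test no clear daily figure

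*Combined protocol and SAP*

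**What the plan says.** Section 7.2.1 of the protocol has three limbs.

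- IMI/REL: "a total daily dose of IMI/REL in excess of 4 g (IMI) + 2 g (REL").
- IMI in Group 2: "a total daily dose of IMI in excess of 4 g per day".
- CMS: "a total daily dose of CMS in excess of the protocol-specified doses in Section 5.2.1.1", with Table 12 named as the reference.

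The first two limits are absolute and do not change with renal function. The third moves with the subject's renal tier.

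Table 12 is titled "Administration Dosage of Loading and Daily Maintenance Doses of CMS According to Renal Function". Its lowest-tier maintenance entry is "75 mg CBA (~180 mg CMS or ~2.3 million IU"), and footnote b says that "the maintenance dose will be administered 12 hours following administration of the loading dose and will be administered every 12 hours thereafter". The entries are therefore amounts per infusion. Table 10 gives the maximum daily maintenance dose as 300 mg CBA and notes that subjects who need a loading dose will receive more than that in the first 24 hours.

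The label has consequences. Under 7.2.1, an overdose without symptoms or abnormal laboratory results is a non-serious ECI, and every overdose must be reported within 24 hours. Table 15 adds: "Any adverse event associated with an overdose is considered a serious adverse event for collection purposes". Section 7.2 counts the active comparator as Sponsor's product, so these rules reach CMS. Table 17 lists serious AEs, and serious drug-related AEs, as Tier 2 parameters with a 95% confidence interval for the difference between arms.

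**The concern.** Two things look wrong.

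**Different bases.** A subject can receive a multiple of the renally adjusted IMI/REL dose without meeting the overdose definition, while a small excess of CMS meets it at once. Section 7.2.1 gives no reason for the difference. The safety of IMI/REL is a primary objective, and the overdose label decides what is reported within 24 hours and, when an AE results, what is classed as serious.

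**No usable daily reference for CMS.** The CMS limb tests a daily total against a table whose title suggests daily doses but whose entries are q12h infusions. A site that takes the listed figure as the daily limit would report correctly dosed Group 2 subjects as overdosed. A site that doubles the figure would not. The same dosing could then be classified differently at different sites.

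**Working it through.** **Inputs.** Single doses by renal tier come from Table 11 (q6h) and Table 12 (q12h). The limits come from 7.2.1. The loading dose is 300 mg CBA (Table 12).

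**Reproducing the plan's own figures.** 500 mg × 4 = 2 g of imipenem per day, which agrees with Section 4.2.2.3: "500 mg, administered IV once every 6 hours (i.e., 2 gram total daily dose"). 150 mg × 2 = 300 mg CBA per day, which agrees with Table 10.

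**Limit relative to assigned dose.** Assigned daily dose = single dose × 4 (IMI/REL, IMI) or × 2 (CMS). Multiple = limit ÷ assigned daily dose. First 24 hours of CMS = 300 + one maintenance dose.

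| CrCl (mL/min) | IMI/REL per day (g) | Multiple at the limit | CMS maintenance per day (mg CBA) | CMS, first 24 h with loading dose (mg CBA) |
|---|---|---|---|---|
| ≥90 | 2.0/1.0 | 4/2.0 = 2.0 | 300 | 450 |
| 60 to <90 | 1.6/0.8 | 4/1.6 = 2.5 | 300 | 450 |
| 30 to <60 | 1.2/0.6 | 4/1.2 = 3.3 | 230 | 415 |
| 15 to <30 | 0.8/0.4 | 4/0.8 = 5.0 | 150 | 375 |

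The relebactam multiples (2 g over 1.0, 0.8, 0.6 and 0.4 g) are the same, as are those for IMI alone. For CMS the multiple is 1.0 in every tier.

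**Upward renal-tier errors.** Both tables are keyed to creatinine clearance, so a wrong tier would ordinarily affect both infusions. There are six ways to dose a subject at a higher tier than the true one. CMS is judged here against the q12h daily total.

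| True tier, dosed as | Imipenem: ratio to assigned; g/day | Over 4 g? | CMS: ratio to assigned; given vs assigned (mg CBA/day) | Over? |
|---|---|---|---|---|
| 60 to <90, as ≥90 | 1.25; 2.0 | No | 1.00; 300 vs 300 | No |
| 30 to <60, as ≥90 | 1.67; 2.0 | No | 1.30; 300 vs 230 | Yes |
| 30 to <60, as 60 to <90 | 1.33; 1.6 | No | 1.30; 300 vs 230 | Yes |
| 15 to <30, as ≥90 | 2.50; 2.0 | No | 2.00; 300 vs 150 | Yes |
| 15 to <30, as 60 to <90 | 2.00; 1.6 | No | 2.00; 300 vs 150 | Yes |
| 15 to <30, as 30 to <60 | 1.50; 1.2 | No | 1.53; 230 vs 150 | Yes |

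None of the six is an IMI/REL or IMI overdose, because the largest Table 11 regimen is half the limit. Five of six are CMS overdoses.

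**Literal reading of the CMS limb.** The listed maintenance figures are 150, 150, 115 and 75 mg CBA. Correct q12h dosing gives 300, 300, 230 and 150 mg per day, twice the listed figure in every tier. The correct first 24 hours (375 to 450 mg) also exceed the 300 mg loading entry. On this reading every correctly dosed CMS subject is overdosed, which conflicts with Table 10.

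**Scale.** For illustration only, one additional SAE among about 18 Group 2 subjects is 1/18 = 5.6 percentage points.

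**The case against.** Drug-specific limits can be defended. Section 4.2.2.3 mentions a 3- to 4-gram daily imipenem dose for severe infections, so 4 g has an anchor in the protocol. For CMS, Section 4.2.2.2 caps maintenance at 300 mg CBA per day and links kidney damage to cumulative dose, so a tighter trigger is understandable. This stands in part: a difference may be justified. But the imipenem figure is for monotherapy of moderately susceptible organisms and covers neither relebactam nor the renal tiers, and 7.2.1 does not cite it.

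A reader might infer that a given dosing error counts only in the comparator arm. The documents do not support that. Group 2's IMI carries the same 4 g limit, so an error confined to the q6h infusion is treated alike in both arms, and an excess beyond the 2.0 to 5.0 multiples counts in both.

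The effect on the analysis may also be small. The SAE route needs an AE that results from the overdose. Overdose ECIs have no row in Table 17, and the Tier 1 events (nephrotoxicity and the two hepatic criteria) do not depend on the overdose label. Events after excess IMI/REL can still be serious on the ordinary criteria, and daily reporting of creatinine clearance to IVRS should limit tier errors. All of this stands.

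On Table 12, footnote b and Table 10 make the intended reading recoverable, so a careful site would double the entries. That is fair, but an operative reporting threshold should not depend on piecing together two tables and a footnote.

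**Conclusion.** The point holds as an inconsistency between drugs. Section 7.2.1 uses a fixed limit of 2.0 to 5.0 times the assigned dose for imipenem-containing therapy and a limit of 1.0 times for CMS. It becomes a difference between arms only because CMS is given in Group 2 alone and the placebo in Group 1 cannot meet the definition. Upward renal-tier errors then give none of six overdoses through IMI/REL or IMI and five of six through CMS.

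A reader might go further and conclude that the serious-AE comparison is biased in favour of IMI/REL. The direction is possible, but the documents give no frequency of dosing errors or of resulting AEs, so the size is unknown and could be nil.

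The Table 12 mismatch is firm on the text: correct dosing exceeds the listed maintenance figure in all four tiers. How sites would in fact read it cannot be known from the documents.

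The figures assume q6h and q12h dosing as scheduled and, for the tier errors, that CMS is judged against the q12h daily total.

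**What to change.** Reconcile 7.2.1 with Tables 10, 11 and 12.

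1. State whether overdose is measured against a fixed daily limit or against the dose assigned for the subject's current renal tier, and use that basis for IMI/REL, IMI and CMS alike. If the bases are to differ, give the reason in 7.2.1. The level of any limit is for the sponsor to decide.
2. Retitle Table 12 as per-infusion doses, or add total-daily-dose figures that include the first 24 hours, and point the CMS limb of 7.2.1 to those figures.

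The cost is a wording change in one section and one table. A possible small downside is a few more overdose ECIs on imipenem-containing therapy. If the sponsor instead loosens the CMS basis, some CMS excesses now reportable as overdoses would no longer be, and the amendment should say so.

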7.2.2 Reporting of Pregnancy and Lactation to the Sponsor

Although pregnancy and lactation are not considered adverse events, it is the responsibility of investigators or their designees to report any pregnancy or lactation in a subject (spontaneously reported to them) that occurs during the trial.

Pregnancies and lactations that occur after the consent form is signed but before randomization must be reported by the investigator if they cause the subject to be excluded from the trial, or are the result of a protocol-specified intervention, including but not limited to washout or discontinuation of usual therapy, diet, placebo treatment or a procedure. Pregnancies and lactations that occur from the time of randomization through 14 days following cessation of Sponsor's product must be reported by the investigator. All reported pregnancies must be followed to the completion/termination of the pregnancy. Pregnancy outcomes of spontaneous abortion, missed abortion, benign hydatidiform mole, blighted ovum, fetal death, intrauterine death, miscarriage and stillbirth must be reported as serious events (Important Medical Events). If the pregnancy continues to term, the outcome (health of infant) must also be reported.

Such events must be reported within 24 hours to the Sponsor either by electronic media or paper. Electronic reporting procedures can be found in the EDC data entry guidelines. Paper reporting procedures can be found in the Investigator Trial File Binder (or equivalent).

7.2.3 Immediate Reporting of Adverse Events to the Sponsor

7.2.3.1 Serious Adverse Events

A serious adverse event is any adverse event occurring at any dose or during any use of Sponsor's product that:

- Results in death;
- Is life threatening;
- Results in persistent or significant disability/incapacity;
- Results in or prolongs an existing inpatient hospitalization;
- Is a congenital anomaly/birth defect;
- Is an other important medical event

Note: In addition to the above criteria, adverse events meeting either of the below criteria, although not serious per ICH definition, are reportable to the Sponsor in the same timeframe as SAEs to meet certain local requirements. Therefore, these events are considered serious by the Sponsor for collection purposes.

- Is a cancer;
- Is associated with an overdose.

Refer to [Table 15](#) for additional details regarding each of the above criteria.

For the time period beginning when the consent form is signed until randomization, any serious adverse event, or follow up to a serious adverse event, including death due to any cause, that occurs to any subject must be reported within 24 hours to the Sponsor if it causes the subject to be excluded from the trial, or is the result of a protocol-specified intervention,

including but not limited to washout or discontinuation of usual therapy, diet, placebo treatment or a procedure.

For the time period beginning at randomization through 14 days following cessation of treatment, any serious adverse event, or follow up to a serious adverse event, including death due to any cause, whether or not related to the Sponsor's product, must be reported within 24 hours to the Sponsor either by electronic media or paper. Electronic reporting procedures can be found in the EDC data entry guidelines. Paper reporting procedures can be found in the Investigator Trial File Binder (or equivalent).

Additionally, any serious adverse event, considered by an investigator who is a qualified physician to be related to the Sponsor's product that is brought to the attention of the investigator at any time outside of the time period specified in the previous paragraph also must be reported immediately to the Sponsor.

All subjects with serious adverse events must be followed up for outcome.

7.2.3.2 Events of Clinical Interest

Selected non-serious and serious adverse events are also known as Events of Clinical Interest (ECI) and must be reported to the Sponsor.

For the time period beginning when the consent form is signed until randomization, any ECI, or follow up to an ECI, that occurs to any subject must be reported within 24 hours to the Sponsor if it causes the subject to be excluded from the trial, or is the result of a protocol-specified intervention, including but not limited to washout or discontinuation of usual therapy, diet, placebo treatment or a procedure.

For the time period beginning at randomization through 14 days following cessation of treatment, any ECI, or follow up to an ECI, whether or not related to the Sponsor's product, must be reported within 24 hours to the Sponsor, either by electronic media or paper. Electronic reporting procedures can be found in the EDC data entry guidelines. Paper reporting procedures can be found in the Investigator Trial File Binder (or equivalent).

Events of clinical interest for this trial include:

1. an overdose of Sponsor's product, as defined in Section 7.2.1 - Definition of an Overdose for This Protocol and Reporting of Overdose to the Sponsor, that is not associated with clinical symptoms or abnormal laboratory results.
2. post baseline laboratory test values that meet the following criteria: an elevated AST or ALT lab value that is greater than or equal to 3X the upper limit of normal and an elevated total bilirubin lab value that is greater than or equal to 2X the upper limit of normal and, at the same time, an alkaline phosphatase lab value that is less than 2X the upper limit of normal, as determined by way of protocol-specified laboratory testing or unscheduled laboratory testing.*

*Note: These criteria are based upon available regulatory guidance documents. The purpose of the criteria is to specify a threshold of abnormal hepatic tests that may require an additional evaluation for an underlying etiology. The trial site guidance for assessment and follow up of these criteria can be found in the Investigator Trial File Binder.

3. a confirmed (i.e., verified by repeat testing) elevated AST or ALT laboratory value that is greater than or equal to $5 \times \text{ULN}$ as a result of within-protocol-specific testing or unscheduled testing.

NOTE: In subjects with pre-existing elevations in transaminase values, only a further elevation that is not anticipated from an underlying medical condition will be considered an ECI. These events may require an additional evaluation for an underlying etiology. The trial site guidance for assessment and follow up of these criteria can be found in the Investigator Trial File Binder.

7.2.4 Evaluating Adverse Events

An investigator who is a qualified physician will evaluate all adverse events with respect to the elements outlined in [Table 15](#). The investigator's assessment of causality is required for each adverse event. Refer to [Table 15](#) for instructions in evaluating adverse events.

Table 15 Evaluating Adverse Events

Maximum Intensity	Mild	awareness of sign or symptom, but easily tolerated (for pediatric trials, awareness of symptom, but easily tolerated)
	Moderate	discomfort enough to cause interference with usual activity (for pediatric trials, definitely acting like something is wrong)
	Severe	incapacitating with inability to work or do usual activity (for pediatric trials, extremely distressed or unable to do usual activities)
Seriousness	A serious adverse event (AE) is any adverse event occurring at any dose or during any use of Sponsor's product that:	
	†Results in death; or	
	†Is life threatening; or places the subject, in the view of the investigator, at immediate risk of death from the event as it occurred [Note: This does not include an adverse event that, had it occurred in a more severe form, might have caused death.]; or	
	†Results in a persistent or significant disability/incapacity (substantial disruption of one's ability to conduct normal life functions); or	
	†Results in or prolongs an existing inpatient hospitalization (hospitalization is defined as an inpatient admission, regardless of length of stay, even if the hospitalization is a precautionary measure for continued observation. (Note: Hospitalization [including hospitalization for an elective procedure] for a preexisting condition which has not worsened does not constitute a serious adverse event.); or	
	†Is a congenital anomaly/birth defect (in offspring of subject taking the product regardless of time to diagnosis); or	
	Is a cancer (although not serious per ICH definition, is reportable to the Sponsor within 24 hours to meet certain local requirements); or	
	Is associated with an overdose (whether accidental or intentional). Any adverse event associated with an overdose is considered a serious adverse event for collection purposes. An overdose that is not associated with an adverse event is considered a non-serious event of clinical interest and must be reported within 24 hours.	
Other important medical events that may not result in death, not be life threatening, or not require hospitalization may be considered a serious adverse event when, based upon appropriate medical judgment, the event may jeopardize the subject and may require medical or surgical intervention to prevent one of the outcomes listed previously (designated above by a †).		
Duration	Record the start and stop dates of the adverse event. If less than 1 day, indicate the appropriate length of time and units	
Action taken	Did the adverse event cause the Sponsor's product to be discontinued?	
Relationship to Sponsor's Product	Did the Sponsor's product cause the adverse event? The determination of the likelihood that the Sponsor's product caused the adverse event will be provided by an investigator who is a qualified physician. The investigator's signed/dated initials on the source document or worksheet that supports the causality noted on the AE form, ensures that a medically qualified assessment of causality was done. This initialed document must be retained for the required regulatory time frame. The criteria below are intended as reference guidelines to assist the investigator in assessing the likelihood of a relationship between the test drug and the adverse event based upon the available information.	
	The following components are to be used to assess the relationship between the Sponsor's product and the AE; the greater the correlation with the components and their respective elements (in number and/or intensity), the more likely the Sponsor's product caused the adverse event:	
	Exposure	Is there evidence that the subject was actually exposed to the Sponsor's product such as: reliable history, acceptable compliance assessment (pill count, diary, etc.), expected pharmacologic effect, or measurement of drug/metabolite in bodily specimen?
	Time Course	Did the AE follow in a reasonable temporal sequence from administration of the Sponsor's product? Is the time of onset of the AE compatible with a drug-induced effect (applies to trials with investigational medicinal product)?
	Likely Cause	Is the AE not reasonably explained by another etiology such as underlying disease, other drug(s)/vaccine(s), or other host or environmental factors

Relationship to Sponsor's Product (continued)	The following components are to be used to assess the relationship between the Sponsor's product and the AE: (continued)	
	Dechallenge	
Was the Sponsor's product discontinued or dose/exposure/frequency reduced? If yes, did the AE resolve or improve? If yes, this is a positive dechallenge. If no, this is a negative dechallenge. (Note: This criterion is not applicable if: (1) the AE resulted in death or permanent disability; (2) the AE resolved/improved despite continuation of the Sponsor's product; (3) the trial is a single-dose drug trial); or (4) Sponsor's product(s) is/are only used one time.)

	Rechallenge	
Was the subject re-exposed to the Sponsor's product in this trial? If yes, did the AE recur or worsen? If yes, this is a positive rechallenge. If no, this is a negative rechallenge. (Note: This criterion is not applicable if: (1) the initial AE resulted in death or permanent disability, or (2) the trial is a single-dose drug trial); or (3) Sponsor's product(s) is/are used only one time.) NOTE: IF A RECHALLENGE IS PLANNED FOR AN ADVERSE EVENT WHICH WAS SERIOUS AND WHICH MAY HAVE BEEN CAUSED BY THE SPONSOR'S PRODUCT, OR IF RE-EXPOSURE TO THE SPONSOR'S PRODUCT POSES ADDITIONAL POTENTIAL SIGNIFICANT RISK TO THE SUBJECT THEN THE RECHALLENGE MUST BE APPROVED IN ADVANCE BY THE U.S. CLINICAL DIRECTOR AND THE INSTITUTIONAL REVIEW BOARD/INDEPENDENT ETHICS COMMITTEE.

	Consistency with Trial Treatment Profile	
Is the clinical/pathological presentation of the AE consistent with previous knowledge regarding the Sponsor's product or drug class pharmacology or toxicology?

The assessment of relationship will be reported on the case report forms /worksheets by an investigator who is a qualified physician according to his/her best clinical judgment, including consideration of the above elements.
		
Record one of the following:	Use the following scale of criteria as guidance (not all criteria must be present to be indicative of a Sponsor's product relationship).	
Yes, there is a reasonable possibility of Sponsor's product relationship.	
There is evidence of exposure to the Sponsor's product. The temporal sequence of the AE onset relative to the administration of the Sponsor's product is reasonable. The AE is more likely explained by the Sponsor's product than by another cause.
	
No, there is not a reasonable possibility of Sponsor's product relationship	
Subject did not receive the Sponsor's product OR temporal sequence of the AE onset relative to administration of the Sponsor's product is not reasonable OR the AE is more likely explained by another cause than the Sponsor's product. (Also entered for a subject with overdose without an associated AE.)
	

